The end of study is defined as the final participant's visit. The Sponsor and the CI have the right at any time to terminate the study for clinical or administrative reasons.

The end of the study will be reported to the Sponsor and REC within 90 days, or 15 days if the study is terminated prematurely. A summary report of the study will be provided to the Sponsor and appropriate REC within 1 year of the end of the study.

REPORTING, PUBLICATION AND NOTIFICATION OF RESULTS

Authorship Policy

Ownership of the data arising from this study resides with the study team and their respective employers. On completion of the study, the study data will be analyzed and tabulated, and a clinical study report will be prepared.

Publication

The clinical study report will be used for publication and presentation at scientific meetings. Investigators have the right to publish orally or in writing the results of the study.

Summaries of the results will also be made available to Investigators for dissemination within their clinical areas (where appropriate and according to their discretion).

PEER REVIEW

Peer review of the initial study approach was performed by 3 peer reviewers. The final version of this study was reviewed by 2 external peer reviewers and 1 internal peer reviewer, who were Autistic individuals with lived or living experience of an ED. The specifics of the study protocol was reviewed by 3 internal peer reviewers with relevant expertise.

REFERENCES

1. American Psychiatric Association. Diagnostic and statistical manual of mental disorders. 5th ed. Arlington, VA: American Psychiatric Publishing; 2013

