Abbreviations: AQ – Autism Spectrum Quotient; ARI – Aberdeen Royal Infirmary; ED – Eating Disorder; EDAC – Eating Disorders and Autism Collaborative;

STUDY POPULATION

The target population for this study includes 25 healthy Autistic individuals and 25 Autistic individuals with AN (aged 25-45). This study will be focusing on an adult sample to ensure individuals are able to articulate longstanding experiences of masking and social camouflage. Participants must also have no contraindications to MRI and have no history of trauma affecting the brain.

INCLUSION CRITERIA

Study Phase 1

- Healthy Autistic Individuals (Autistic Controls) must:
 - Be aged 25-45 years
 - Be Autistic (clinically diagnosed and/or have an AQ-10 score of ≥ 6)
 - Be able to provide informed consent for the study
 - Be able to read, understand and respond to questionnaires in English
 - Have no history of an ED
 - Willing to have an MRI scan in Aberdeen
- Autistic Individuals with AN (Autistic individuals with AN) must:
 - Be aged 25-45 years
 - Be Autistic (clinically diagnosed and/or have an AQ-10 score of ≥ 6)
 - Be able to provide informed consent to the study
 - Be able to read, understand and respond to questionnaires in English
 - Have a diagnosis of AN or a BMI of < 18.5
 - Willing to have an MRI scan in Aberdeen

EXCLUSION CRITERIA

- Individuals are not eligible for the study if they:
 - Are aged < 25 or > 45 years
 - Are not Autistic or not clinically diagnosed as Autistic and have an AQ-10 score of < 6
 - Are diagnosed with an ED other than AN
 - Have a history of brain injury (e.g., stroke)
 - Be unable to provide informed consent for the study
 - Have contraindications to MRI scanning, such as implantable cardiac devices
 - Are unable to read, understand and respond to questionnaires in English
 - As participants will need to consent to the study and complete questionnaires by themselves, individuals with intellectual disability will be excluded from this study

The Autism Spectrum Quotient (AQ-10) is a short questionnaire that primary care practitioners can use to test if a person should be referred for an autism assessment. We will use this as a screening tool to confirm the presence of Autistic traits in addition to the presence of a clinical diagnosis.

PARTICIPANT SELECTION AND ENROLMENT

IDENTIFYING PARTICIPANTS FOR ELIGIBILITY

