Individuals will be considered an Autistic control if they meet study eligibility criteria and have no previous or current history of an ED and have no contraindications to MRI. Potential participants will be considered an Autistic individual with an ED if they meet study eligibility criteria and have a current diagnosis of AN and have no contraindications to MRI. Clinical members of the Eating Disorders Services (EDS) at NHS Grampian will assist with recruitment by identifying patients who are Autistic and have AN. This will involve review of medical records by the direct care team.

Once potential participants have been identified, a pre-recruitment screening survey will ask all participants to:

- 1) Confirm they have received a clinical diagnosis of autism,
- 2) Confirm if they are an Autistic individual with AN or not
- 3) Complete the AQ-10
- 4) List their height and weight
- 5) Confirm if they have a previous history of trauma affecting the brain
- 6) Confirm if they have any contraindications to MRI such as a heart pace-maker.

For both groups, potentially eligible participants will be given a standard participant information sheet, and a simplified pictorial participant information sheet. If eligible to participate, all participants will also be given an MRI Information Pack to familiarise themselves with the on-site location and process associated with an MRI scan.

Participant who meets the inclusion criteria will be then asked whether they would prefer to receive their consent form and questionnaires electronically or complete them in-person just before their MRI scan. All participants will provide informed consent before completing the questionnaires and having their MRI scan. The MRI scan will be scheduled with the participant at their convenience. If the participant misses their study visit, they will be contacted by the research team to reschedule their scan. If 1) participants complete the pre-recruitment screener and are not eligible to participate or 2) participants are deemed eligible but the recruitment limit of n=50 has been reached, they will be informed that they will not be able to take part, and will be thanked for their time and interest. With permission, all participants' GPs will be informed of their participation.

Autistic Controls:

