Autistic controls will also be recruited by advertising the study to the public through adverts, flyers, press releases and on social media. Recruitment via this approach will also include those from third sector charities who have not previously flagged that they would like to be contacted for future research. All advertising material will contain a QR code and a link which will redirect participants to the pre-recruitment screener to determine eligibility to participate in the study. If participants are deemed eligible to participate, they will receive the participant eligibility confirmation letter, and the participant information sheet (PIS). Once individuals have read the PIS and confirm their participation, the research team will correspond with the participant to schedule their study visit and MRI scan and the participant will receive the MRI information pack.

Autistic Individuals with AN:

Autistic Individuals with AN will be recruited through the EDS team within NHS Grampian, North East Eating Disorder Support (NEEDS), BEAT Eating Disorders, Autism & Neurodiversity North Scotland (A-ND) and Scottish Women's Autism Network (SWAN) and by advertising the study to the public through adverts, flyers, press releases and on social media, and through members of the Eating Disorders and Autism Collaborative (EDAC) Research network who have previously notified their interest to participate in future eating disorder and autism related research.

Recruitment via Third Sector Charities & The EDAC Network:

Individuals from third sector charities and the EDAC network who have previously flagged that they would like to be contacted for future research will receive a participant invitation letter. Contact information of the research team will be included with the invitation letter to reach out to the research team if they have any questions. Individuals will also receive the PIS and a link to a participant pre-recruitment screening survey to determine study eligibility. If

participants are deemed eligible to participate, they will receive the participant eligibility confirmation letter. Once individuals confirm their participation, the research team will correspond with the participant to schedule their study visit and MRI scan and the participant will receive the MRI Information Pack.

Recruitment via Third Sector Charities & the public:

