Data generated from this study will be kept for a minimum of 10 years and [name] will act as custodian for the data. Contact details, upon provision of consent by participants, will be kept up to 5 years for the purposes of conducting future ethically-approved research. Otherwise they will be deleted at the end of the study. All data in electronic form will be retained and archived in secure University of Aberdeen servers. All data in physical or paper form will be retained in a secure locked drawer associated with this study within [name] at the University of Aberdeen. Only the named members of the research team (see Study Management and Oversight) will be able to access this data.

The sponsor is responsible for ensuring that study data is archived appropriately. Documents will be archived in line with the Sponsor's standard operating procedures.

DATA PROTECTION

All data collected through Qualtrics will be securely stored on servers compliant with the UK data protection laws and other international privacy standards, ensuring robust protection of personal information. Qualtrics adheres to strict data privacy policies, including data encryption, de-identification and anonymisation, both in transit and at rest. Qualtrics also has role-based access controls and ensures that only authorised members of the research team involved in the project will have access to the data to effectively safeguard participant data.

A member of the clinical care team will access medical records for the purposes of reviewing medical data relevant to participant eligibility, including age, date of birth, diagnosis of AN, diagnosis of Autism, and history of trauma affecting the brain. This information will only be seen by members of the individual's direct care team.

The chief investigator (CI) and study staff involved with this project will comply with the requirements of the UK Data Protection Laws. The HRA recommended wording to fulfil transparency requirements under the GDPR for health and care research has been included in the participant information sheet.

The CI and study staff will also adhere, if appropriate, to the current version of the NHS Scotland Code of Practice on Protecting Patient Confidentiality. Access to collated participant data will be restricted to the CI and appropriate study staff.

Computers used to collate the data will have limited access measures via usernames and passwords.

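### Outside the NHS route, AN status rests on a self-report screener item, and the protocol provides no variable or data flow that marks confirmed cases

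*Protocol*

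**What the plan says.** **Group rule.** The Protocol, under Identifying Participants for Eligibility, counts someone as an Autistic individual with an ED if they meet the eligibility criteria and "have a current diagnosis of AN and have no contraindications to MRI". The Inclusion Criteria are worded differently: "Have a diagnosis of AN or a BMI of < 18.5".

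**Record check.** Eating Disorders Services staff at NHS Grampian help by identifying patients: "This will involve review of medical records by the direct care team". Data Protection lists what is reviewed, "including age, date of birth, diagnosis of AN, diagnosis of Autism, and history of trauma affecting the brain", and then states: "This information will only be seen by members of the individual's direct care team".

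**Other routes.** AN participants are also recruited through charities, the EDAC network and "by advertising the study to the public through adverts, flyers, press releases and on social media". No record check is described for them.

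**What the research team receives.** Everyone completes the pre-recruitment survey. Its items on AN status and body size are "Confirm if they are an Autistic individual with AN or not" and "List their height and weight". Under Study Assessments, participants later report co-occurring EDs, length of ED illness, medication, height and weight, and complete the EDE-Q.

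**Use of the grouping.** Under Proposed Analyses, aim 1 compares brain structure and function between the groups and aim 2 compares CAT-Q scores. Sample Size justifies 25 per group by the wish to estimate effect sizes for planning later studies.

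**The concern.** The variable that defines the comparison in aims 1 and 2 is the least well verified one at entry. Autism status has a diagnosis question and a second instrument, the AQ-10, which Study Assessments also uses to detect participants who are not genuine. So the protocol foresees false entrants, but the AQ-10 cannot detect a false or outdated AN declaration.

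If some people in the AN group do not have current AN, the group difference is no longer the one the rule describes. A pilot whose product is effect sizes would pass that error on to the next study. A natural check is to see whether the result holds in cases whose diagnosis was confirmed, and the protocol makes no provision for identifying them.

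This is more than detail left to an analysis plan. What participants consent to, and what information may pass from the clinical team to the researchers, has to be settled before enrolment. If confirmation is neither consented to nor collected, no later plan can recover it.

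**Working it through.** The protocol gives no misclassification rate, effect size or number expected by route, so there is no figure of its own to reproduce. The main check is textual; the arithmetic only shows scale.

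**1. Follow AN status into the research data, by route.**

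| Route | Record check described | How AN status reaches the researchers |
|---|---|---|
| NHS Grampian | Yes, by the clinical team; content stays with that team | Screener item; the team's invitation implies a positive check |
| Charities, EDAC network | None | Screener item |
| Adverts, flyers, press, social media | None | Screener item |

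No step returns even a yes/no result to the study team. Neither the listed screener items nor the listed questionnaires include recruitment route. Subject logs are kept (Data Collection), but their fields are not given.

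**2. Set the screener item against the rule.** The rule needs a diagnosis that is current. As listed, item 2 asks only whether the person is an Autistic individual with AN. Someone with past AN, or with self-identified AN, could answer yes in good faith.

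**3. Ask what the other data can do.** BMI, illness duration and the EDE-Q are self-reported. They allow a plausibility check but do not establish a diagnosis. Under the Inclusion Criteria, a person with a diagnosis may have a BMI of 18.5 or more, and a person below 18.5 may have no diagnosis.

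**4. Size of the dilution (assumed inputs).** Let d be the true difference in SD units, m the share of the AN group without current AN, and r how far those people lie from the control mean towards the AN mean (r = 0: like controls; r = 1: like AN cases).

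Observed difference = d × [1 − m(1 − r)]

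With d = 0.8:

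| m | r = 0 | r = 0.5 |
|---|---|---|
| 10% | 0.8 × 0.90 = 0.72 | 0.8 × 0.95 = 0.76 |
| 20% | 0.8 × 0.80 = 0.64 | 0.8 × 0.90 = 0.72 |
| 30% | 0.8 × 0.70 = 0.56 | 0.8 × 0.85 = 0.68 |

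The values of d, m and r are all assumptions. I give no power figures, because the pilot sets no power target.

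**5. Precision of an analysis in confirmed cases.** With k confirmed cases against 25 controls and SD 1, the 95% half-width is 1.96 × √(1/25 + 1/k).

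| k | Half-width (SD) |
|---|---|
| 5 | 0.96 |
| 10 | 0.73 |
| 15 | 0.64 |
| 20 | 0.59 |
| 25 | 0.55 |

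The number of confirmed cases to expect is not stated.

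**The case against.** A reader might infer that the research team can never learn who was checked, and that confirmed cases therefore cannot be analysed separately. The documents do not support that. Under Recruitment via NHS Grampian, the care team identifies the patient and hands over the invitation. The researchers then carry out steps written for that route, including sending the information sheet a second time and informing the GP. Data Protection limits who sees the record content; it does not conceal that the clinical team made the approach. Nothing forbids logging the route. This stands, and it limits the point to what the protocol fails to provide. Route would still be an imperfect marker, because an NHS patient may also answer a poster or a public advert.

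Further objections, and what remains of them:

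- **Silence is not absence.** The lists of screener items and questionnaires do not claim to be a full data dictionary, and sensitivity analyses commonly belong in an analysis plan. That is fair for the route variable. It does not answer the consent and data-flow gap.
- **Misclassified cases need not resemble controls.** Controls must never have had an ED, whereas someone wrongly declaring current AN may have past AN or undiagnosed restriction. This stands: r = 0 is the extreme of the range between the two group means, and the bias could be small.
- **Reach is limited.** The primary objective concerns masking, ED symptoms and brain structure, and the mediation model uses the whole sample. Neither needs the AN label. This stands and confines the effect to aims 1 and 2.
- **The remedy is not clean.** Confirmed cases may be more severely ill or more often in treatment, and they will be few. This stands, so the comparison is a sensitivity check only.

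**Conclusion.** The point holds in a limited form. The AN group is defined by a current diagnosis. Outside the NHS route, membership rests on a self-report item that asks for neither a diagnosis nor its currency. The one record check stays with the clinical team, and the protocol lists no variable and describes no data flow that would mark confirmed cases.

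The effect is possible bias in the aim 1 and aim 2 differences, probably towards zero. Its size cannot be derived from the documents. Under an assumed true difference of 0.8 SD, the loss is 0.08 to 0.24 SD if 10% to 30% of the group resemble controls, and half that if such cases lie midway between the groups. That is smaller than the sampling uncertainty at 25 per group (about 0.55 SD either way), but it is systematic and would carry into planning figures. It would be wrong to say the effects will be too small: the text establishes neither the number of misclassified cases nor their likeness to controls.

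Separately, the Inclusion Criteria (diagnosis or low BMI) and the assignment rule (current diagnosis) disagree, so some eligible people may have no diagnosis to confirm. This is an inexpensive improvement worth making before enrolment and not a flaw that invalidates the study.

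**What to change.** 1. Reword screener item 2 to ask whether the person has a clinical diagnosis of AN and whether it is current.
2. Record in the subject log the recruitment route and the basis of AN status: confirmed diagnosis, self-declared diagnosis, or BMI criterion only. The third category prevents someone without a diagnosis being filed as an unconfirmed one.
3. Add an optional consent item allowing the eating disorder service or the GP to return a yes/no answer on current AN diagnosis. Amend Data Protection so that, with consent, this answer alone may reach the study team. No one need be excluded because of it.
4. Report aims 1 and 2 for the whole AN group, and repeat them in confirmed cases as a sensitivity analysis with confidence intervals.
5. Reconcile the Inclusion Criteria with Identifying Participants for Eligibility. Which rule should apply is for the sponsor and the clinical team to decide.

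**Cost.** One survey wording change, two log fields, one consent item, a reply line in the GP contact already planned with permission, a protocol amendment and one repeat analysis. Some replies will be missing, and the confirmed subset will be smaller and less precise. It may also differ in severity, so a difference between the two analyses will not by itself measure misclassification.

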Neuroanatomical Differences Associated with Anorexia Nervosa and Masking Behaviour in Autistic Individuals

Sponsor	University of Aberdeen
Funder	Eating Disorders and Autism Collaborative (EDAC); UK Research and Innovation (UKRI)
Chief Investigator	[name]
Sponsor number	2-081-24
Version Number and Date	Version 2, 20 th May 2025

PROTOCOL APPROVAL

Neuroanatomical Differences Associated with Anorexia Nervosa and Masking Behaviour in Autistic Individuals

Signatures

By signing this document I am confirming that I have read, understood and approve the protocol for the above study.

Chief Investigator

Name: [name]
Postdoctoral Researcher
Address: School of Medicine, Medical Sciences and Nutrition
University of Aberdeen
[name]
[name]
Aberdeen
[name]

[contact]
[contact]
E-mail: [contact]

Sponsor

Institution: University of Aberdeen
Address: Research Governance Office
[name]
[name]
Aberdeen
[name]

[contact]

LIST OF ABBREVIATIONS

AN	Anorexia Nervosa
AQ	Autism Quotient
ASRS	Adult Attention Deficit Hyperactivity Disorder Self-Report Scale
CAT-Q	Camouflaging Autistic Traits Questionnaire
CI	Chief Investigator
CSOG	Clinical Studies Oversight Group
ED	Eating Disorder
EDAC	Eating Disorder and Autism Collaborative
EDE-Q	Eating Disorder Examination Questionnaire
EDS	Eating Disorders Service
HADS	Hospital Anxiety and Depression Scale
ITQ	International Trauma questionnaire
LSAS	Leibowitz Social Anxiety Scale
MQ	Monotropism Questionnaire
MRI	Magnetic resonance imaging
REC	Research Ethics Committee
ROI	Region of Interest
R&D	Research and Development
UKRI	UK Research and Innovation
WSAS	Work and Social Adjustment Scale

PROTOCOL SUMMARY

CONSIDERED FOR ENTRY	Autistic individuals (either self-diagnosed or clinically diagnosed) as controls and Autistic individuals with a restrictive eating disorder (ED) such as anorexia nervosa (AN). Participants will be aged 25-45.
TRIAL ENTRY	Autistic individuals with and without AN will be screened for eligibility. Either online or written informed consent will be sought prior to the study.
MAIN AIMS OF STUDY	The main aim of the study is to determine whether there are neuroanatomical or functional differences between Autistic individuals relative to Autistic individuals with AN, and whether Autistic individuals with AN exhibit higher masking behaviour than Autistic individuals without AN.
CO-ORDINATION	Local and Overall: overseen by the Chief Investigator
FUNDER	EDAC; UKRI

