Autistic controls will be recruited by advertising the study to third sector charities such as Autism & Neurodiversity North Scotland (A-ND) and Scottish Women's Autism Network (SWAN) and by bulk email to the University of Aberdeen's Neurodiversity Network facilitated by leads of this network, and to members of the Eating Disorders and Autism Collaborative (EDAC) Research network who have previously notified their interest to participate in future autism-related research. Autistic controls who self-report an autism diagnosis will be confirmed as eligible to participate upon completion of the AQ-10 with a cut-off score of ≥ 6 . All potential participants will complete the pre-recruitment screening survey to determine eligibility for the study.

Recruitment via Third Sector Charities & The EDAC Network:

Individuals from third sector charities and the EDAC network who have previously flagged that they would like to be contacted for future research will receive a participant invitation letter. Contact information of the research team will be included with the invitation letter to reach out to the research team if they have any questions. Individuals will also receive the participant information sheet (PIS) and a link to a participant pre-recruitment screening survey to determine study eligibility. If participants are deemed eligible to participate, they will receive the participant eligibility confirmation letter. Once individuals confirm their participation, the research team will correspond with the participant to schedule their study visit and MRI scan, and the participant will receive the MRI Information Pack.

Recruitment via Third Sector Charities & the public:

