Published results will not contain any personal data that could allow identification of individual participants.

PROPOSED ANALYSES

Methods of analysis will include assessment of demographic characteristics, brain structure and functional connectivity patterns, as well as calculation of generalised linear models between characteristics of masking and brain structure, as well as between characteristics of masking and symptoms of eating disorders. Pre-processing of MRI scans will utilise the FreeSurfer and fMRIprep software packages for brain structure and function respectively. Regions of interests (ROIs) will be derived from normalisation to the standard Desikan-Killiany atlas. All statistical analyses will be conducted using the R Software.

To achieve aim 1, structural differences of brain regions, both global and specific ROIs, will be reported as mean \pm standard deviation (in mm³) for each ROI between groups. For functional differences an independent component analysis approach will be used via the CONN toolbox on the statistical parametric mapping (SPM) software package, reported in Z-scores for incorporated components, and means \pm standard deviations of component loadings. Neuroimaging-based findings will also be accompanied by determining any group-based differences across demographic and questionnaire-derived information.

To achieve aim 2, mean differences on scores derived from the CAT-Q will be compared across groups and will be reported as mean \pm standard deviation.

To achieve aim 3, linear models will be used to evaluate associations between brain structure and function and domains of social camouflage (particularly masking behaviour), as well as associations between levels of masking and the presence of reported anxiety, depression, work and social adjustment and trauma. A 3-path mediation model will also assess whether ROI-based brain structure mediates the relationship between masking behaviour and ED symptomatology within the entire sample.

The statistical analysis will be conducted by the Chief Investigator (CI; [name]), and an Autistic peer researcher and PhD student ([name]). The statistical plan was developed by the CI and [name].

MISSING DATA

Where appropriate, missing data will be imputed to minimise the loss of data. Depending on the type of data missing, either simple imputation, multiple imputation will be used to minimise data loss.

EARLY STOPPING

No interim analysis is planned to inform early stopping.

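### The aim 1 structural comparison is stated only as mean ± SD in mm³ by group; adding a group difference adjusted for age, sex and head size would be a cheap improvement

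*Protocol*

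**What the plan says.** Proposed Analyses gives the structural part of aim 1 in one sentence, which covers both whole-brain and regional measures. The summary it specifies is the group mean together with its "standard deviation (in mm³) for each ROI between groups". No test, model or covariate is attached to this contrast.

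Other text that bears on the point:

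- **Models (Proposed Analyses).** Generalised linear models are assigned to masking with brain structure and to masking with eating disorder symptoms. For aim 3, "linear models will be used to evaluate associations between brain structure and function and domains of social camouflage", and a mediation model follows. None of these is the AN-versus-control contrast.
- **Normalisation (Proposed Analyses).** The ROIs "will be derived from normalisation to the standard Desikan-Killiany atlas". This says how regions are defined. It is not described as a head-size correction.
- **Demographics (Proposed Analyses).** "Neuroimaging-based findings will also be accompanied by determining any group-based differences across demographic and questionnaire-derived information".
- **Groups (Study Population).** The target "includes 25 healthy Autistic individuals and 25 Autistic individuals with AN (aged 25-45"). Both groups share the age limits. Neither randomisation nor matching applies.
- **Recruitment (Participant Selection and Enrolment).** A-ND, SWAN, the EDAC network and public advertising serve both groups. The NHS Grampian eating disorder service, NEEDS and BEAT are listed only for the AN group. The "bulk email to the University of Aberdeen's Neurodiversity Network" is listed only for controls.
- **Covariates collected (Study Assessments).** The demographic questionnaire lists gender and age, but not sex.
- **Purpose.** The Protocol Summary says: "The main aim of the study is to determine whether there are neuroanatomical or functional differences between Autistic individuals" with and without AN. Sample Size justifies 25 per group by effect-size estimation for later studies. The Primary Objective, under Study Aims and Objectives, is the association among masking, eating disorder symptoms and brain structure.

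**The concern.** Regional volumes in mm³ scale with head size, and head size differs between the sexes. In a comparison of groups defined by diagnosis, nothing in the design makes sex mix or head size equal. If they differ, the group difference in mm³ carries that difference whether or not AN is related to the volume.

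Comparing demographics beside the imaging results alerts the reader to an imbalance, but the estimate stays as it was. Age matters less, because both groups are restricted to 25-45. The shared recruitment sources also limit how far the groups are likely to diverge.

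What is at stake is the use the protocol makes of the result. The sample is meant to yield effect sizes for planning. Sampling error shows in a confidence interval, but confounding does not, so a confounded effect size can be carried forward unnoticed.

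**Working it through.** There is no plan figure to reproduce: the protocol gives no alpha, power, effect size, SD or expected sex mix. The only input from the document is 25 per group. Everything else is an assumption, shown as a range. Volumes are in within-sex SD units.

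**1. Bias from sex mix.** Bias = (difference in share of women) × (sex difference in ROI volume). Assumed sex difference: 0.5 to 1.1 SD.

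| Women, one group vs the other | Calculation | Bias (SD) |
|---|---|---|
| 90% vs 90% | 0 × 0.5 to 0 × 1.1 | 0 |
| 90% vs 80% | 0.10 × 0.5 to 0.10 × 1.1 | 0.05 to 0.11 |
| 90% vs 75% | 0.15 × 0.5 to 0.15 × 1.1 | 0.075 to 0.165 |

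**2. Bias from head size alone.** With equal sex mix, an assumed head-size gap of 0.2 SD and an assumed correlation of 0.3 to 0.6 between ROI and intracranial volume: 0.2 × 0.3 = 0.06 to 0.2 × 0.6 = 0.12 SD.

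**3. Set against sampling error.** The standard error is √(2/25) = 0.28 SD, and the 95% half-width is t(0.975; 48 df) × √(2/25) = 0.57 SD. The share of mean squared error due to bias is bias² / (bias² + 0.08):

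- 0.05 SD: 0.0025 / 0.0825 = 3%
- 0.11 SD: 0.0121 / 0.0921 = 13%
- 0.165 SD: 0.0272 / 0.1072 = 25%

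**4. Effect on planning, in both directions.** Assume a true difference of 0.50 SD and a next study sized on the pilot's point estimate (two-sided 5%, 80% power, t-test).

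| Estimate used (SD) | n per group | True power at 0.50 SD |
|---|---|---|
| 0.665 (inflated by 0.165) | 37 | 56% |
| 0.55 (inflated by 0.05) | 53 | 72% |
| 0.50 (no bias) | 64 | 80% |
| 0.45 (deflated by 0.05) | 79 | 88% |
| 0.335 (deflated by 0.165) | 141 | 99% |

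**5. What adjustment does.** Simulation at 25 per group with the sex effects and correlations above and an assumed sex difference in intracranial volume of 1.2 SD:

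- The unadjusted bias matches step 1.
- With age, sex and intracranial volume in the model, the bias falls to within about 0.01 SD. This is expected, because the simulated confounding runs only through those covariates.
- At 90/80 and 90/75, the standard error is 0.23 to 0.29 SD adjusted, against 0.28 to 0.31 unadjusted.
- At 95% versus 50% women with a correlation of 0.3, adjustment costs a little precision: about 0.32 against 0.29 SD.
- Adjusting for age and intracranial volume without sex leaves a bias of −0.07 to +0.02 SD at 90/80 and −0.10 to +0.03 SD at 90/75. This is why sex itself should be available.

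**The case against.** The strongest objection is one of scope. The choice of covariates and of a model per ROI is ordinary SAP content, and an SAP may exist. The aim 1 sentence also describes how results are reported. For aim 2, the same section separates comparing from reporting, and its opening list of methods is not exhaustive. This much stands: a reader might infer that the protocol commits to an unadjusted analysis or rules adjustment out, and it does not say so. The point survives because the protocol does state how aim 1 will be achieved, names models for other questions but not for this contrast, and can be improved at little cost.

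A second objection is weight. Every input to the bias is assumed, several recruitment sources are shared, and the illustrated bias is well below the sampling error. That stands in full and sets the size of the claim.

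Third, a reader might infer that the next study would be underpowered. The documents fix neither the direction of any imbalance nor that of the true effect, so a study that is too large is as possible as one that is too small. Nor does the protocol say that the next study would be sized on the point estimate.

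Fourth, a reader might take the primary objective to be at risk. It concerns the association among masking, symptoms and brain structure. The structural group contrast belongs to the main aim in the Protocol Summary but is not that objective.

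Last, the absence of sex from a one-line list of questionnaire items does not show that sex goes unrecorded. Neither the questionnaire nor the MRI safety screener is shown.

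**Conclusion.** The point holds as a cheap improvement. As stated, the aim 1 structural contrast has no protection against differences in sex mix or head size between non-randomised, unmatched and partly differently sourced groups. The planned demographic comparison would reveal such differences without correcting for them.

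Whether there is any bias depends on the sample obtained, and balanced groups give none. The 0.05 to 0.17 SD illustrated for moderate imbalance rests on an assumed sex effect of 0.5 to 1.1 SD. Larger values need extreme imbalance. The documents do not support saying that the aim 1 result will be biased. They support saying only that the stated method leaves a known source of confounding in place when most of the data needed to remove it are already being collected.

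**What to change.** Keep the mean ± SD in mm³ by group. Add one sentence to Proposed Analyses under aim 1: for each ROI volume, the group difference with its 95% CI will be estimated from a linear model with group, age, sex and FreeSurfer estimated intracranial volume, leaving out the last term where intracranial volume is itself the outcome. Make sure that sex is recorded as well as gender. If an SAP already specifies such a model, align the aim 1 sentence with it.

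The cost is wording and, if sex is not already captured, one questionnaire item. Age is collected, and intracranial volume can be taken from the planned FreeSurfer processing. The model uses three degrees of freedom (48 to 45). Precision usually improves, with a small loss only where sex imbalance is extreme and head size predicts the ROI weakly. Confounding through anything other than these three covariates would remain.
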